5.12.2. Non-AED Concomitant Medications and Non-Drug Therapy/Procedures

Prior and concomitant medications taken during the study will be coded using the World Health Organization (WHO) dictionary (Version: Global B3, March 2024 or higher). Each concomitant medication will be classified as either an anti-epileptic (AED) or a non-AED medication. Non-AED prior and concomitant medications will be summarized by frequency of drug classification and generic drug name. Prior and concomitant medications will be presented in a data listing. The drug classification will be the anatomic therapeutic chemical (ATC) classification 4. If this classification is not present, the next available classification will be utilized.

Prior and concomitant non-drug therapy/procedures will be coded using MedDRA Version 27.1 or higher. Concomitant non-drug therapy/procedures will be summarized by frequency of SOC and PT. Prior and concomitant non-drug therapy/procedures will be presented in a data listing.

5.12.3. Concomitant AED Medication and Therapy/Procedures

Concomitant AED medications will be summarized by frequency of drug classification and generic drug name.

5.12.4. Clinical Laboratory Assessments

Descriptive summaries of selected (quantitative) clinical laboratory results and change from baseline will be presented by visit. Change from double-blind baseline will be summarized by visit. Additionally, for hematology, blood chemistry, coagulation, and urinalysis parameters, toxicity grade will be determined for laboratory tests with toxicity grade specified in [Section 9.4](#). Shifts from baseline to greatest (worst) treatment-emergent laboratory toxicity will be presented. For parameters not graded by CTCAE, laboratory values outside the normal range for each parameter will be identified using shift tables. Each subject's hematology, blood chemistry, and quantitative urinalysis values will be flagged as "low" (below the lower limit of normal/LLN), "normal" (within the normal range), or "high" (above the upper limit of normal/ULN) relative to the normal ranges of the central laboratory. In addition, the shift from baseline to the maximum post-baseline value and the minimum post-baseline value for each laboratory test.

The number and percentage of subjects who have post-baseline elevations in liver transaminase (alanine aminotransferase [ALT] or aspartate aminotransferase [AST]) or bilirubin abnormalities in relation to fold above the upper limit of normal will be summarized according to the Food and Drug Administration's Premarketing Clinical Evaluation on Drug-Induced Liver Injury Guidance for Industry ([FDA 2009](#)).

Abnormal hepatic laboratory values will be categorized and evaluated for any occurrence among all post-baseline assessments (where “and” in the bulleted list below indicates elevations occurring at the same visit). Within each laboratory parameter grouping, a subject may be counted once per elevation criteria using the worst-case result. That is, a subject with a worst case ALT elevation $> 5 \times$ the ULN would be counted once in the ALT $> 3 \times$ ULN category and once in the ALT $> 5 \times$ ULN category, regardless of how many ALT elevations the subject had that met the $> 5 \times$ ULN and $> 3 \times$ ULN elevation criteria.

- ALT and/or AST $> 3 \times$ ULN and total bilirubin > 1.5 or $2 \times$ ULN at the same visit at the same visit
- AST $> 3, 5, 10, 20 \times$ ULN
- ALT $> 3, 5, 10, 20 \times$ ULN
- Total bilirubin $> 1.5, 2 \times$ ULN
- Alkaline phosphatase (ALP) $> 1.5 \times$ ULN

In addition, an eDISH plot, a shift plot showing liver safety panel tests over time (baseline vs. post-baseline), and distribution plots of ALT, AST, ALP, and bilirubin over time will be produced to aid identification of any potential cases (Merz M. et. al. 2014). The plots to be included are the scatter plot of maximum transaminase versus maximum bilirubin, the liver test safety panel over time, and the distribution of ALT by time. The distribution plots for AST, ALP, and bilirubin will use the same format as used for ALT.

5.12.5. Vital Signs

Vital sign measurements will include body temperature (oral or tympanic), respiratory rate, systolic blood pressure, diastolic blood pressure, and heart rate. Body temperature, blood pressures, and heart rate will be measured with the subject in a sitting/semi-recumbent position after a 5-minute rest. For the body temperature, the same method must be used for all measurements for each individual subject and should be the same for all subjects at each investigational site. Vital signs and corresponding changes from extension baseline will be summarized by visit using descriptive statistics. Change from double-blind baseline will be summarized by visit using descriptive statistics.

Out of range vital signs occurring post-baseline will be summarized.

The following out-of-range criteria will be summarized for post-baseline assessments:

- Systolic Blood Pressure (Supine)
 - < 90 mmHg
 - > 140 mmHg
- Diastolic Blood Pressure (Supine)
 - < 50 mmHg
 - > 90 mmHg

- Heart Rate (Supine)
 - < 60 bpm
 - > 100 bpm
- Respiratory Rate
 - < 12 bpm
 - > 20 bpm
- Temperature
 - < 36° C
 - > 38° C

Vital signs results will be listed.

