### **8.3.2     *Vital Sign Measurements***

Vital sign measurements will include body temperature, respiratory rate, systolic blood pressure, diastolic blood pressure, and heart rate.

Vital signs will be measured with the subject in a sitting/semi-recumbent position after 5 minutes rest.

A properly sized and calibrated blood pressure cuff will be used to measure blood pressure each time. The use of an automated device for measuring blood pressure and heart rate is acceptable, although, when done manually, heart rate will be measured in the brachial/radial artery for at least 30 seconds. When the timing of these measurements coincides with a blood collection, blood pressure and heart rate should be obtained prior to the nominal time of the blood collection.

Body temperature will be measured with either an oral (temperature taken at floor of the mouth) or tympanic thermometer. The same method (ie, oral or tympanic) must be used for all measurements for each individual subject and should be the same for all subjects.

Any clinically relevant changes occurring during the trial will be recorded in the AE section of the eCRF.

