2. OBJECTIVES AND ENDPOINTS

The trial objectives and endpoints are summarized in [Table 2](#).

Table 2. Objectives and Endpoints

Objectives	Endpoints
Primary: To assess the long-term safety and tolerability of CVL-865 as adjunctive therapy in subjects with focal onset seizures	
• Nature, frequency, and temporality of treatment-emergent adverse events (AE) (nonserious and serious), including abuse-related AEs and AEs related to medication handling irregularities• Clinically significant changes in electrocardiogram (ECG), vital sign measurements, clinical laboratory assessments, and physical and neurological examination results• Suicidality assessed using the Columbia- Suicide Severity Rating Scale (C-SSRS)• Withdrawal symptoms assessed using the Modified Clinical Institute Withdrawal Assessment – Benzodiazepines (mCIWA-B)
Exploratory: To assess the long-term efficacy of CVL-865 as adjunctive therapy in subjects with focal onset seizures	
• Focal onset seizure frequency per week over the Maintenance Phase• Seizure freedom• Seizure rate over time• Patient Global Impression of Change (PGI-C) score at each trial visit• Change from Baseline in Clinical Global Impression – Severity (CGI-S) score at each trial visit
Exploratory: To evaluate the plasma exposure of CVL-865	
• Summary listing of CVL-865 concentrations by dose and visit

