3.2.2.1. Treatment-emergent Laboratory Abnormality

A treatment-emergent laboratory abnormality is defined as value outside the normal range which occurs on or after the start of IMP through the last follow up contact. Where applicable, these abnormalities will be graded.

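### The out-of-range vital-sign counts ignore each subject's baseline and name a body position the trial does not use, and the treatment-emergent laboratory definition has no baseline or worsening condition

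*SAP*

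**What the plan says.** Among the endpoints under the primary objective, SAP section 2 lists "Clinically significant changes in electrocardiogram (ECG), vital sign measurements, clinical laboratory assessments, and physical and neurological examination results".

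For vital signs, SAP 5.12.5 summarizes change from the extension and double-blind baselines by visit with descriptive statistics. It then adds a categorical display: "Out of range vital signs occurring post-baseline will be summarized". The list of limits is introduced with "The following out-of-range criteria will be summarized for post-baseline assessments". The limits include systolic pressure below 90 or above 140 mmHg, heart rate below 60 or above 100 bpm, and temperature below 36 °C or above 38 °C. No baseline condition, change criterion or shift table goes with them.

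The limits for systolic pressure, diastolic pressure and heart rate carry a position label, for example "Systolic Blood Pressure (Supine" (closing bracket omitted). The same section says "Body temperature, blood pressures, and heart rate will be measured with the subject in a sitting/semi-recumbent position after a 5-minute rest". Protocol 8.3.2 agrees: "Vital signs will be measured with the subject in a sitting/semi-recumbent position after 5 minutes rest". SAP 3.2.5 says the same.

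For laboratory tests, SAP 3.2.2.1 says: "A treatment-emergent laboratory abnormality is defined as value outside the normal range which occurs on or after the start of IMP", and the window runs through the last follow-up contact. Nothing requires a normal or less abnormal value before dosing.

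**The concern.** All subjects receive CVL-865 and there is no concurrent comparator, so each subject's own earlier value is the main reference for judging drug effect. A count that ignores it puts a subject with habitual bradycardia or existing hypertension in the same cell as one who developed the finding on treatment. Mean changes by visit do not repair this, because a mean can hide individual shifts in both directions.

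The term treatment-emergent in 3.2.2.1 promises emergence or worsening, and the definition does not deliver it. The position label is a contradiction inside one section and leaves the programmer and the reader unsure what the limits apply to.

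**Working it through.** The plan gives no figure to reproduce. SAP 5.3 states no hypothesis, and the figure of about 120 subjects in SAP 1.2 is an expected rollover number. The check compares the planned displays and then illustrates the size.

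**1. Categorical safety displays side by side**

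| Measure | Planned display | Uses baseline? |
|---|---|---|
| Vital signs (SAP 5.12.5) | Post-baseline value beyond a fixed limit | No |
| QTcF (5.12.6) | Absolute bands, plus change of >30 to ≤60 and >60 msec | Yes, through the change bands |
| Graded laboratory tests (5.12.4) | Shift from baseline to worst grade | Yes |
| Ungraded laboratory tests (5.12.4) | Shift tables | Yes |
| Each laboratory test (5.12.4) | Shift to maximum and to minimum post-baseline value | Yes |
| Liver multiples of ULN (5.12.4) | Any post-baseline occurrence | No, but a baseline versus post-baseline liver shift plot is planned |
| Suicidal ideation against recent history (9.2) | Score above 0 and higher than baseline | Yes |

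Vital signs are the measure with no categorical or graphical display tied to baseline.

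**2. Position.** Three of the five vital signs (systolic pressure, diastolic pressure, heart rate) are labelled supine. Respiratory rate, temperature and the laboratory tests are not. Protocol 8.3.2, SAP 3.2.5 and the opening of SAP 5.12.5 all give sitting/semi-recumbent.

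**3. Laboratory definition.** Take a value equally out of range before and after the first dose. Under 3.2.2.1 it is treatment-emergent. In the 5.12.4 shift tables it falls on the diagonal and can be told apart from a new abnormality. The label is wrong, but most of the planned tables still separate the two.

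**4. Illustration of size.** Inputs: N = 120 (SAP 1.2). The share b already out of range on a criterion at baseline and unchanged, and the share q of the rest newly out of range, are both assumptions.

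- Count under 5.12.5 = N·b + N·(1 − b)·q
- New cases only = N·(1 − b)·q
- Pre-existing share = N·b ÷ count

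| b | Unchanged (N·b) | q = 5%: count / new / pre-existing share | q = 10%: count / new / pre-existing share |
|---|---|---|---|
| 5% | 6 | 11.7 / 5.7 / 51% | 17.4 / 11.4 / 34% |
| 10% | 12 | 17.4 / 5.4 / 69% | 22.8 / 10.8 / 53% |
| 20% | 24 | 28.8 / 4.8 / 83% | 33.6 / 9.6 / 71% |
| 30% | 36 | 40.2 / 4.2 / 90% | 44.4 / 8.4 / 81% |

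Example, b = 10%, q = 5%: 120 × 0.10 + 120 × 0.90 × 0.05 = 12 + 5.4 = 17.4, and 12 ÷ 17.4 = 69%.

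**5. Which baseline.** SAP 4.1.11 sets the extension baseline as the last value before IMP in SZ-002. Subjects who took CVL-865 7.5 or 25 mg BID in SZ-001 were on drug at that point. A rule tied to that baseline alone would classify an abnormality that arose on drug in SZ-001 and persisted as pre-existing. The double-blind baseline is needed as well.

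**The case against.** **Clinically significant change has another route.** Protocol 9.4.1 makes the frequency and severity of adverse events the primary safety analysis. Protocol 8.3.2 has clinically relevant vital-sign changes recorded as adverse events, and Appendix 3 (Table 10) covers abnormal findings that worsen from baseline and are judged clinically significant. This stands. A reader might infer that the primary safety table cannot separate new events from background; the documents do not support that. What remains is narrower: the one categorical summary of measured vital signs does not show change.

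**The vital-sign table is not called treatment-emergent.** True. Change from both baselines is also summarized by visit and all results are listed. But these are averages and listings, and neither counts how many subjects moved out of range.

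**Laboratory reporting already uses baseline.** This stands too. A reader of 3.2.2.1 might infer that laboratory abnormalities are reported on the post-dose value alone. SAP 5.12.4 rules that out for graded and ungraded tests, leaving the definition and the liver counts.

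**The supine label is only a label.** A reader might infer that a program selecting supine records would find none. The documents describe no position field and no selection by position, so that is speculation. The contradiction itself is plain.

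**Counting only subjects in range at baseline could hide worsening.** This is correct and shapes the fix. A systolic pressure going from 142 to 190 mmHg is above 140 at both times, so such a rule would drop it and a shift table alone would show no shift. Likewise, SAP 9.4 leaves platelets, bicarbonate and eosinophils ungraded, so a clause relying on higher grade could never register further worsening in them. Protocol 2.3 names decreased hematologic parameters as an important potential risk.

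**Conclusion.** The point holds on three counts. The vital-sign out-of-range counts disregard baseline in a single-arm trial. The position label on three of five vital signs contradicts both documents. The treatment-emergent laboratory definition lacks a baseline or worsening condition, a fault mainly of definition.

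The size cannot be fixed from the documents. With 5% to 30% of 120 subjects assumed out of range on a criterion at baseline and unchanged, 6 to 36 of them enter its count. They would make up 51% to 90% of it if 5% of the rest are newly out of range, and 34% to 81% if 10% are. These shares show the mechanism and are not forecasts.

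The effect is on the reading of descriptive safety tables. It does not undermine the adverse-event analysis.

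**What to change.** 1. **SAP 5.12.5, displays.** Keep the any-post-baseline counts. Add, per parameter, a shift table of baseline category (low, within, high) by worst post-baseline category, against both the extension and the double-blind baseline. Run the low and high directions separately, as 5.12.4 does with minimum and maximum. For subjects already out of range at baseline, also show the maximum change, so that worsening stays visible.
2. **SAP 5.12.5, label.** Replace the supine label on the blood pressure and heart rate criteria with sitting/semi-recumbent.
3. **SAP 3.2.2.1.** Define treatment-emergent as outside the normal range on or after the first dose and either within range at baseline or worsened from baseline. Worsened means a higher grade for graded tests, and further from the normal limit in the same direction for ungraded tests such as platelets. Show the result against both baselines.

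The liver multiples-of-ULN counts can stay as they are, read beside the planned liver shift plot.

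The cost is SAP wording and a few extra tables from data already planned for collection, before database lock.

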5.12.6. Electrocardiograms (ECGs)

ECGs measurements and corresponding changes from extension baseline will be summarized by visit using descriptive statistics. Change from double-blind baseline will be summarized by visit using descriptive statistics.

The number and percentage of subjects who experience any post-baseline occurrence of potentially clinically significant corrected QT values using Fridericia's method (QTcF) will be summarized. These presentations will include QTcF values > 450 msec to ≤ 480 msec, > 480 msec to ≤ 500 msec, and > 500 msec; or changes of > 30 msec to ≤ 60 msec or > 60 msec. Important abnormalities in ECG waveform that are changes from baseline readings will also be reported in a listing.

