1.1. Study Overview

[figure not shown]
This is a 57-week, active-treatment, open-label extension trial designed to assess the long-term safety and tolerability of CVL-865 as adjunctive therapy in subjects with focal onset seizures. Enrollment into the trial will consist of eligible subjects who completed the Maintenance Phase of Trial CVL-865-SZ-001.

Eligible subjects will enter this trial directly after completing Visit 4 (end of Maintenance Phase) of Trial CVL-865-SZ-001. The efficacy and safety assessments from Visit 4 of Trial CVL-865-SZ-001 will serve as the baseline assessments for the open-label trial for any assessments that are not unique to the open-label trial. All subjects must provide informed consent to participate in the open-label trial before any baseline assessments that are unique to the open-label trial are performed.

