1.4. Treatment Period

Titration Phase:

Following enrollment in Trial CVL-865-SZ-002, subjects will enter a 2-week double-blind Titration Phase. Based on the blinded treatment group subjects were assigned to in Trial CVL-865-SZ-001, the dose will be increased in weekly intervals during the double-blind Titration Phase to a final dose of 25 mg BID as shown in table (Table 1). Subjects who completed the Maintenance Phase of Trial CVL-865-SZ-001 on a dose of 25 mg BID will remain on this dose (blinded) for the Titration Phase of Trial CVL-865-SZ-002.

Subjects who terminate during the double-blind Titration Phase (before Day 15) should receive 3 weeks of IMP to complete the Taper Phase.

Maintenance Phase:

Subjects will continue to receive treatment with CVL-865 25 mg BID throughout a 52-week Maintenance Phase. However, this daily dose of CVL-865 can be reduced to 17.5 mg BID to address tolerability issues upon investigator discretion. Following the Maintenance Phase, subjects will be tapered off investigational medicinal product (IMP) over 3 weeks in weekly intervals. A summary of the dosing schedule is provided in table below ([Table 1](#)).

A summary of the dosing schedule is provided below ([Table 1](#)).

Table 1. Summary of the Dosing Schedule

	Blinded Titration Phase		Maintenance Phase	Taper Phase		
Dose in Trial CVL-865-SZ-001	Day 1	Day 8	Day 15-Day 379	Day 386	Day 393	Day 400
Duration	2 weeks		52 weeks	3 weeks		
Placebo	5 mg BID	12.5 mg BID	25 mg BID	17.5 mg BID	10 mg BID	5 mg BID
CVL-865 7.5 mg BID	12.5 mg BID	17.5 mg BID	25 mg BID	17.5 mg BID	10 mg BID	5 mg BID
CVL-865 25 mg BID	25 mg BID	25 mg BID	25 mg BID	17.5 mg BID	10 mg BID	5 mg BID
Not applicable			17.5 mg BID ^a	10 mg BID	5 mg BID	2.5 mg BID

Abbreviations: BID = twice daily.

^a Subjects who had their dose reduced to 17.5 mg BID due to tolerability reasons during the Maintenance Phase

Follow-up Phase:

Follow-up telephone contact will be performed 7 ± 3 days after the last dose of IMP. A Safety Follow-up Visit will be made approximately 4 weeks after last dose of IMP.

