4.1.11. Extension Baseline Value

For purposes of analysis, the baseline value is defined as the last value obtained prior to initiation of IMP in CVL-865-SZ-002 (e.g. the Study Day 1 value). Should the Day 1 visit value be obtained after the first dose of IMP or if this value is not available at Day 1, then the most recent value obtained prior to earliest initiation of IMP will be used for the baseline value.

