4.1.14. Change from Baseline (Extension)

Change from baseline for a given endpoint is defined as the value on a given Study Day (time point) minus the Baseline Value.

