5. STATISTICAL ANALYSIS METHODS

5.1. General Considerations

Descriptive statistical methods will be used to summarize the data from this trial. Unless stated otherwise, the term “descriptive statistics” refers to number of subjects (N), number of observations (n), arithmetic mean, median, standard deviation (SD), first quartile (Q1), third quartile (Q3), minimum, and maximum for continuous data, and frequencies and percentages for categorical data. Certain figure presentations will include the standard error of the mean (SE). The term “treatment group” refers to treatment assignment in Trial CVL-865-SZ-001: Placebo, 7.5 mg BID CVL-865, 25 mg BID CVL-865 and assignment in Trial CVL-865-SZ-002: 25 mg BID CVL-865. All data collected from subjects who sign the informed consent form, including screen failures, will be included in data listings. Unless otherwise noted, the data listings will be sorted first by treatment, subject number and then by date within each subject number.

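### QTcF change categories and laboratory shift tables default to a baseline that is on drug for the SZ-001 active arms, so effects already present at rollover are under-counted

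*SAP*

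**What the plan says.** SAP 4.1.11 sets the default: "the baseline value is defined as the last value obtained prior to initiation of IMP in CVL-865-SZ-002". SAP 4.1.14, headed as the extension version, adds that "Change from baseline for a given endpoint is defined as the value on a given Study Day (time point) minus the Baseline Value". A separate double-blind baseline, and change from it, are defined in SAP 4.1.10 and 4.1.15.

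The extension baseline falls at the end of SZ-001 dosing: "Eligible subjects will enter this trial directly after completing Visit 4 (end of Maintenance Phase) of Trial CVL-865-SZ-001" (SAP 1.1). The rollover groups are described as "treatment assignment in Trial CVL-865-SZ-001: Placebo, 7.5 mg BID CVL-865, 25 mg BID CVL-865" (SAP 5.1). Under SAP 1.4 and its Table 1, the 25 mg group keeps its dose through the blinded titration, the 7.5 mg group is raised to 25 mg BID, and the placebo group starts drug.

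For ECGs, SAP 5.12.6 summarizes change from both baselines by visit; for the second it says "Change from double-blind baseline will be summarized by visit using descriptive statistics". It then counts subjects in absolute QTcF bands (above 450, 480 and 500 msec) and subjects with "changes of > 30 msec to ≤ 60 msec or > 60 msec". That last item names no baseline.

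For laboratory data, SAP 5.12.4 also plans by-visit change from the double-blind baseline. The categorical output is described only as "Shifts from baseline to greatest (worst) treatment-emergent laboratory toxicity will be presented", with normal-range shift tables for tests that are not graded.

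**The concern.** Clinically significant ECG and laboratory changes are part of the primary endpoint, and Protocol 2.3 names bone marrow suppression and falling hematologic parameters as important potential risks. The outputs that count individual subjects with large changes are the QTcF categories and the shift tables. If their reference value was taken after a completed course of the same drug, part or all of the drug effect is subtracted before counting starts.

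The SAP does not treat other measures this way. Treatment-emergent C-SSRS categories are compared with the double-blind baseline and/or lifetime history (SAP 5.12.9), and CGI-S change is shown from both baselines (SAP 5.11.2). No reason is given for leaving the ECG and laboratory categories with one.

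**Working it through.** The trial is descriptive, so the plan has no figure to reproduce. The check has three parts.

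**1. Which effect is removed, by SZ-001 group (SAP Table 1)**

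| SZ-001 group | Dose at extension baseline | Maintenance dose | Effect removed |
|---|---|---|---|
| Placebo | none | 25 mg BID | none |
| 7.5 mg BID | 7.5 mg BID | 25 mg BID | the part present at 7.5 mg |
| 25 mg BID | 25 mg BID | 25 mg BID | all that is present at Visit 4 |

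The SZ-001 allocation is not in the documents. Of about 120 expected rollovers, equal arms (assumed) would put 80 on drug at extension baseline, 40 of them on 25 mg. Across assumed ratios 1:1:1, 2:1:2, 1:1:2 and 2:1:1 (placebo : 7.5 : 25), 60 to 90 are on drug and 30 to 60 on 25 mg.

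**2. QTcF illustration**

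A single subject (assumed values): double-blind baseline 410, extension baseline 435, extension maximum 445 msec.
- From the double-blind baseline: 445 − 410 = +35, in the >30 to ≤60 category.
- From the extension baseline: 445 − 435 = +10, in no category.
- Absolute: 445 is below the 450 cut.

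At one on-treatment visit in the 25 mg arm, P(change > 30) = 1 − Φ((30 − d)/SD), where d is the mean effect not subtracted by the baseline. Assume a 10 msec effect at 25 mg BID, so d = 10 from the double-blind baseline and d = 0 from the extension baseline:
- SD 12: 1 − Φ(1.67) = 4.8% against 1 − Φ(2.50) = 0.6%
- SD 16: 1 − Φ(1.25) = 10.6% against 1 − Φ(1.88) = 3.0%
- SD 20: 1 − Φ(1.00) = 15.9% against 1 − Φ(1.50) = 6.7%

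The SAP counts any post-baseline occurrence. Protocol Tables 2 and 3 schedule six post-baseline ECGs (Visits 3, 5, 8, 11, 15 and 16). Simulation assumptions: effect proportional to dose (10 msec at 25 mg, 3 at 7.5 mg, 2 at the 5 mg BID end-of-taper dose for Visit 16); independent within-visit SD equal to SD of change/√2; all six ECGs done; no dose reductions. Chance of any change above 30 msec:

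| SZ-001 group | SD of change | Double-blind baseline | Extension baseline |
|---|---|---|---|
| 25 mg | 12 | 16% | 3% |
| 25 mg | 20 | 43% | 22% |
| 7.5 mg | 12 | 16% | 10% |
| 7.5 mg | 20 | 43% | 36% |
| Placebo | 12 | 16% | 16% |
| Placebo | 20 | 43% | 43% |

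With 40 subjects in the 25 mg arm, SD 12 gives 0.16 × 40 ≈ 6 against 0.03 × 40 ≈ 1. SD 20 gives 0.43 × 40 ≈ 17 against 0.22 × 40 ≈ 9. With no drug effect the two baselines give the same rate. In this model all three groups have the same maintenance effect, yet from the extension baseline the group with the longest 25 mg exposure has the fewest counted changes.

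**3. Laboratory shifts**

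Exclusion 6 (Protocol 5.2) is set against the grades in SAP 9.4:

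| Test | Excluded at Visit 1 | Grade 2 begins |
|---|---|---|
| Hemoglobin, g/dL | <10 (women), <11 (men) | <10 |
| WBC, ×10⁹/L | <3.0 | <3.0 |
| Neutrophils, ×10⁹/L | <2.0 | <1.5 |

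An eligible subject is therefore at most Grade 1 on these tests at extension baseline, and a later Grade 2 value shows as a shift from either baseline. What can be lost is the step from Grade 0 to Grade 1. Example with an assumed LLN of 4.0: WBC 5.0 at double-blind baseline, 3.5 at extension baseline (eligible), worst value 3.1. That is Grade 0 to 1 from the first baseline and Grade 1 to 1 from the second. For neutrophils even this needs an LLN above 2.0. Platelets are not graded. Exclusion 6 sets no numerical limit for other graded tests such as lymphocytes or transaminases.

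**The case against.** The strongest reply is that much of this information is reported elsewhere. SAP 5.1 defines descriptive statistics to include quartiles, minimum and maximum. The largest QTcF rise from the double-blind baseline will therefore be printed at each visit, and the corresponding laboratory summary can show the largest fall. Absolute QTcF bands, worst toxicity grades, liver-test multiples of ULN and the out-of-range definition in SAP 3.2.2.1 do not depend on an off-drug reference, apart from part of the creatinine grading. A shift table also displays the baseline grade. All of this stands. A reader might infer that effects begun in SZ-001 are hidden; the documents do not support that. What is missing is the number of subjects affected.

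A reader might also infer that someone whose neutrophils fell markedly in SZ-001 would be counted as unchanged. Exclusion 6 would ordinarily keep that subject out. Protocol 8.1 refers results that arrive after enrollment to the medical monitor, so the limit is nearly but not strictly complete.

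Third, SAP 5.12.6 mentions both baselines just before the QTcF categories, so the extension baseline is an inference there. It is the one the SAP's own definitions lead to, and if another was meant the text still needs to say so.

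Finally, Protocol 9.4.1 sets the extension baseline and makes presentations from the SZ-001 baseline optional, and SZ-001 assesses safety itself. The choice is thus permitted. But SZ-001 cannot supply cumulative counts over the further year of dosing.

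**Conclusion.** The point holds as under-counting in specific tables. By default definition, the QTcF change categories and the laboratory shifts subtract any effect already present at SZ-001 Visit 4: fully for the 25 mg arm, partly for 7.5 mg, not for placebo. For hemoglobin, WBC and neutrophils the graded loss is essentially the Grade 0 to 1 step.

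The size for QTcF is unknown. Protocol 4.3 reports no ECG changes at doses up to 100 mg, so there may be nothing to mask. The 16 to 43% against 3 to 22% for the 25 mg arm shows only how far the two baselines could diverge if a 10 msec effect existed; effect, SD and dose-proportionality are all assumed. It should not be read as evidence of a QTcF effect, nor applied to all rollovers from active arms. No comparable figure can be derived for laboratory shifts.

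**What to change.** In SAP 5.12.6, state which baseline the QTcF change categories use, and produce them from the double-blind baseline as well as the extension baseline. In SAP 5.12.4, do the same for the toxicity-grade shifts and the normal-range shift tables. Show all of them by SZ-001 treatment group, so that placebo rollovers, whose two baselines are both off drug, can be read beside the active-arm rollovers.

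This is a free improvement. The double-blind baseline is already defined and already used for the by-visit summaries, and the protocol allows such presentations. The cost is a set of duplicate tables, with no new data and no change to trial conduct. It should be settled before database lock.
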